**8.6 Definitions of Response to ASN002**

**8.6.1 Relapsed/Refractory Lymphomas**

The 2014 Lugano Classification will be used to document disease response or progression in subjects with DLBCL, MCL, FL, or PTCL (**28**).

**8.6.2 Solid Tumors**

The RECIST 1.1 criteria will be used to document disease response or progression in subjects with advanced/metastatic solid tumors (**29**).

**8.6.3 Myelofibrosis**

The International Working Group-Myeloproliferative Neoplasms Research and Treatment (IWG-MRT) criteria will be used to document disease response or progression in subjects with myelofibrosis (**30**)

**8.6.4 Chronic Lymphocytic Leukemia**

The International Workshop on Chronic Lymphocytic Leukemia (**31**) will be used to document disease response or progressions in subjects with CLL. For patients with persistent lymphocytosis, a partial response in all other measures will be defined as a partial response with lymphocytosis (**33**).

**8.6.5 Clinical Disease Progression**

Clinical disease progression can be characterized by loss of appetite, weight loss, change in bone pain/worsening bone pain, increased use of analgesics, cachexia/decrease in performance scale (e.g., an increase in the subject's ECOG score) and other symptoms of progressive neoplastic disease.

The investigator will evaluate the integrated results of all these parameters and based on this evaluation will decide if a subject has clinical progression.

## **9 SELECTION AND WITHDRAWAL OF SUBJECTS**

### **9.1 Subject Inclusion Criteria**

In order to be eligible to participate in the study, subjects must meet the following criteria:

1. Written informed consent obtained prior to any study-related procedure being performed;
2. Male or female subjects at least 18 years of age at the time of consent;
3. ECOG Performance Status 0-2;
4. Radiographically evaluable tumor by 2014 Lugano Classification recommendations (lymphomas) or RECIST 1.1 (advanced solid tumors);
5. Recovered from the reversible effects of prior antineoplastic therapy (with the exception of alopecia and Grade 1 neuropathy). Screening blood counts of the following:
  - a. Absolute neutrophil count  $\geq 1000/\mu\text{L}$ ,
  - b. Platelets  $\geq 75,000/\mu\text{L}$ ,
  - c. Hemoglobin  $\geq 8 \text{ g/dL}$  (with transfusion support);
6. Screening chemistry values of the following:
  - a. Alanine aminotransferase (ALT) and aspartate transaminase (AST)  $\leq 3.0 \times$  upper limit of the normal reference range (ULN),
  - b. Total bilirubin  $\leq 1.5 \times$  ULN,
  - c. Creatinine  $\leq 1.5 \times$  ULN;
7. At screening, life expectancy of at least 3 months;
8. Subject is willing and able to comply with all protocol required visits and assessments;
9. Male and female subjects of child-bearing potential must agree to use medically acceptable methods of birth control throughout the study and for thirty (30) days after the last dose of study medication.
10. Subjects must have one of the following disease characteristics

(Part A only)

- a. Histologically or cytologically confirmed metastatic and/or advanced solid tumors or lymphomas for which no standard therapy exists, or who are not eligible for standard treatment. Subjects must have received at least one prior therapy for their malignancy;

(Part A or B only)

Lymphomas

- b. Histologically confirmed DLBCL/MCL/FCL/PTCL on the basis of excisional lymph node or extranodal tissue biopsy;

- c. Diagnosis of relapsed/refractory DLBCL/MCL/FL/PTCL defined as 1) recurrence of disease after a CR, or 2) PR, SD at completion of treatment regimen preceding entry into study. Subjects must have received at least one regimen of treatment for lymphoma.
- d. Subjects must not be candidates for standard therapy.
- e. Subjects who have not received SCT must be ineligible to receive SCT.

(Part B only)

Primary Myelofibrosis

- f. Confirmed diagnosis of PMF, post-PV MF, or post-ET MF according to the 2008 WHO criteria (30),
- g. High risk or intermediate-2 risk or symptomatic intermediate-1 risk as defined by Dynamic International Prognostic Scoring System (DIPSS), see **Appendix D**
- h. Palpable splenomegaly at least 5 cm below the left costal margin,
- i. Known JAK2 mutational status,
- j. Refractory/relapsed, or intolerant to prior JAK2 therapy in the judgement of the investigator.

Chronic Lymphocytic Leukemia

- k. Confirmed diagnosis of B-cell CLL, according to the International Workshop on Chronic Lymphocytic Leukemia (IWCLL) (31)
- l. Measurable disease defined as lymphocytosis  $> 5,000/\mu\text{L}$ , or at least one palpable or CT measurable lesion ( $> 2.0 \text{ cm}$ ), or quantifiable bone marrow involvement.
- m. Active disease requiring treatment as defined by IWCLL consensus criteria
- n. Relapsed or refractory disease or intolerant to a maximum of 2 prior systemic therapies. One of the prior regimens must have included a purine analog and/or an alkylating agent.

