# **11 ASSESSMENT OF EFFICACY**

## **11.1 Primary Efficacy Variable**

### **11.1.1 Disease Response**

It is expected that the investigator will choose the most appropriate method for radiographic assessment of the individual subject's disease status. Subjects with a diagnosis of lymphoma are expected to undergo CT (for non-FDG-avid lymphoma), or PET-CT (for FDG-avid lymphoma) for their efficacy evaluation. Subjects with advanced or metastatic solid tumors are expected to undergo CT with contrast (unless medically contraindicated) or MRI for their efficacy evaluation.

For patients with MF spleen measurement will be performed by palpation and by MRI (preferred) or CT scan.

For patients with CLL a baseline CT scan of chest/abdomen/pelvis and a bone marrow aspirate and biopsy are desirable.

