### 5.2 Efficacy Population (EP)

The efficacy population (EP) will include all subjects who have an evaluable screening and post-dose tumor assessment. The EP will be used as the supportive analysis population for summaries and analyses of the efficacy endpoints. No EP will be reflected if Part B is not completed for at least one indication.

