### **8.3 Protocol Deviations**

Major protocol deviations are defined to be those deviations that could potentially bias either efficacy or safety summaries of the study. Subjects associated with major protocol deviations will be identified prior to database lock.

Major deviations from the clinical protocol may include, but are not limited to:

- Subjects that were administered at least one dose of ASN002 and who did not satisfy the inclusion/exclusion criteria.
- Subjects meeting conditions for withdrawal that were not withdrawn.
- Subjects that received a prohibited concomitant medication.
- Repeated non-compliance in administration of study drug, as monitored by the study site at the assessment timepoints shown within Table 1 of Section 3.2, where non-compliance is less than 80% or greater than 105% of expected administration of study drug.

The number and percentage of subjects with major deviations and the number of deviations will be summarized by type of violation and overall. Summaries will be provided by treatment cohort and overall. The denominators for calculating percentages will be based on the number of subjects in the analysis population for each treatment cohort and overall.

Major protocol deviations will be provided in a data listing by subject.

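### Inclusion criterion 4 was not adapted for myelofibrosis and CLL: read literally, 14 to 28 of 84 Part B subjects fail it and could be left out of the primary efficacy population

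*Protocol*

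**What the plan says.** The lead-in to protocol 9.1 binds all subjects: "In order to be eligible to participate in the study, subjects must meet the following criteria". Criterion 4 in that list is "Radiographically evaluable tumor by 2014 Lugano Classification recommendations (lymphomas) or RECIST 1.1 (advanced solid tumors". The synopsis repeats it. Neither place has an MF or CLL branch or an *if applicable*.

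Criterion 10 then sets disease requirements by indication. For MF, 10h asks for "Palpable splenomegaly at least 5 cm below the left costal margin". For CLL, 10l begins "Measurable disease defined as lymphocytosis", offers a palpable or CT-measurable lesion as an alternative, and ends "or quantifiable bone marrow involvement". So a CLL subject can qualify on blood or marrow alone. Imaging at baseline is not mandatory in CLL (protocol 11.1.1): "For patients with CLL a baseline CT scan of chest/abdomen/pelvis and a bone marrow aspirate and biopsy are desirable".

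On the analysis side, SAP 5.2 defines the Efficacy Population (EP) as "all subjects who have an evaluable screening and post-dose tumor assessment". SAP 5.3 takes the Per Protocol (PP) population as the EP without major deviations and makes it primary for efficacy. SAP 8.3 gives, among its examples of what a major deviation may be, "Subjects that were administered at least one dose of ASN002 and who did not satisfy the inclusion/exclusion criteria". SAP 9.1.1 applies the Part B binomial test to all six cohorts, MF and CLL included, and defines a responder by Lugano CR or PR only.

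**The concern.** The amendment that added MF and CLL added 10f-n but left criterion 4 as it was. Two rules in one list now disagree on who is eligible. A subject with a palpable spleen, or with CLL shown only in blood or marrow, satisfies criterion 10 and fails criterion 4 on its literal words.

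This reaches the analysis because the primary efficacy population depends on eligibility. Whether 14 MF subjects and an unknown number of CLL subjects count in the primary analysis rests on how criterion 4 is read, and no rule settles it. Major deviations are identified before database lock. The study is open-label with analyses run on an ongoing basis (protocol 15.10, SAP 12), so the reading could be chosen with responses already known. Protocol section 15 gives the SAP priority where the two differ, but the SAP does not resolve the point.

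**Working it through.** **Step 1. Compare the rules by disease.**

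| Rule | Lymphoma | Solid tumors | MF | CLL |
|---|---|---|---|---|
| Criterion 4 | Lugano | RECIST 1.1 | none named | none named |
| Disease requirement in criterion 10 | biopsy-confirmed, relapsed/refractory | advanced or metastatic | palpable spleen (10h) | blood, lesion or marrow (10l) |
| Response criteria, protocol 8.6 and 11.1.1 | Lugano | RECIST 1.1 | IWG-MRT/ELN | IWCLL |
| Responder for the SAP 9.1.1 test | Lugano CR/PR | no Part B test | Lugano CR/PR | Lugano CR/PR |

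Protocol 8.6.1 assigns Lugano to DLBCL, MCL, FL and PTCL only. The MF spleen scan at baseline and week 24 (protocol Table 2, disease-assessment footnote) is not described as a Lugano or RECIST assessment, so it does not meet criterion 4 literally.

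**Step 2. Follow the route to the primary population.** Fails criterion 4, then possible major deviation (SAP 8.3), then outside PP (SAP 5.3). The first link is literal text, the second is permissive, and the third follows by definition. The EP definition is a separate matter: it names neither imaging nor Lugano nor RECIST. It does not say whether palpation, the symptom form or blood counts are a tumor assessment. An MF subject who leaves before week 24 with palpation data only is therefore neither clearly in nor clearly out.

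**Step 3. Count.** Inputs: 6 cohorts of 14 (protocol 15.1, SAP 4), so 6 × 14 = 84.

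- MF failing on the strict reading: 14.
- CLL failing: 0 to 14. The documents give no split.
- Total affected: 14 + 0 = 14 to 14 + 14 = 28.
- Left in the primary population from this cause alone: 84 − 28 = 56 to 84 − 14 = 70.

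**Step 4. Effect on the test.** The plan states type I error 0.02 and power 0.9 for at least 3 responses in 14, with rates 0.05 and 0.4. The exact binomial gives:

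- P(X ≥ 3 | 14, 0.05) = 1 − (0.95^14 + 14·0.05·0.95^13 + 91·0.05²·0.95^12) = 1 − (0.4877 + 0.3593 + 0.1229) = 0.030
- P(X ≥ 3 | 14, 0.4) = 1 − (0.6^14 + 14·0.4·0.6^13 + 91·0.4²·0.6^12) = 1 − (0.0008 + 0.0073 + 0.0317) = 0.960

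The stated pair is not reproduced. That is a separate matter and does not bear on this point.

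For CLL, assume a number n remaining in PP and use the SAP rule of one-sided p < 0.05 against 0.05, with power taken at 0.4:

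| n in PP (assumed) | Smallest rejecting count | Exact type I error | Power |
|---|---|---|---|
| 5 | 2 | 0.023 | 0.66 |
| 10 | 3 | 0.012 | 0.83 |
| 12 | 3 | 0.020 | 0.92 |
| 14 | 3 | 0.030 | 0.96 |

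For MF on the strict reading, n = 0 and there is no primary-population test.

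**The case against.** The strongest reply is that criterion 4 limits itself. Its parentheses tie Lugano to lymphoma and RECIST to solid tumors, and MF and CLL have their own entry items. On this view, nobody would read criterion 4 so as to cancel 10h and 10l. This is probably what the sponsor meant, and it is why the point is an inconsistency and not a flaw in the design. But the text does not say it. Where the protocol limits a criterion by disease it does so openly, as in the headings of criterion 10 and the MF exception in exclusion 16.

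Second, exclusion is a judgement. SAP 8.3 says *may include* and describes major deviations as those able to bias the summaries. Protocol 15.9 provides a pre-lock review of whether subjects with deviations belong in each analysis. This stands. A reader might infer that these subjects would be dropped, or that the MF primary population would be empty. The documents support only that they could be.

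Third, a reader might infer that the EP itself demands a radiographic tumor. It does not. Protocol Table 2 schedules disease-specific assessments for MF and CLL at screening and after dosing, and nothing says that these fail the EP definition.

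Fourth, an empty MF set needs a loose reading at enrolment and a strict one later. That is a fair criticism of the extreme case, but the two decisions are separate: the investigator confirms eligibility on Day 1 (protocol 10.2.1), and deviations are judged before lock. Read strictly throughout, the conflict appears at screening instead, because MF subjects could not be enrolled.

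**Conclusion.** Criterion 4 contradicts the MF and CLL entry criteria and must be reconciled with them. The strict reading affects 14 to 28 of 84 Part B subjects. The upper figure, 28/84 = 33%, is the combined size of the two cohorts and should not be read as the expected loss.

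This rests on full enrolment of 14 per cohort and on the strict reading being applied at the deviation review. It also needs Part B to be completed for at least one indication, since otherwise SAP 5.2, 5.3 and 9 drop the EP and PP and report listings only. The CLL power figures rest on assumed numbers.

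It would be too strong to say that the Part B primary objective fails for these cohorts. Safety and tolerability use the safety population and are untouched. A subject lost from PP only by the deviation route stays in the EP, which is also analysed as supportive.

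The Lugano-only responder definition in SAP 9.1.1 is the firmer SAP defect. It depends on no choice of reading, and it would leave the MF and CLL tests without a matching endpoint even if criterion 4 were repaired.

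**What to change.** Make three wording changes together:

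1. **Protocol 9.1 and synopsis, criterion 4.** State that it applies to lymphoma and solid-tumor subjects, and that evaluable disease for MF and CLL is as already defined in 10f-j and 10k-n. The synopsis letters these items e-i and j-m, so the cross-reference must match in each place.
2. **Synopsis, protocol 15.2 and SAP 5.2 (and the SAP definitions page).** Replace *tumor assessment* with *disease assessment by the response criteria for that cohort*, naming Lugano, RECIST 1.1, IWG-MRT/ELN and IWCLL.
3. **SAP 9.1.1.** Define MF responders by IWG-MRT/ELN and CLL responders by IWCLL. List the categories that count, including whether clinical improvement counts in MF and whether partial response with lymphocytosis counts in CLL.

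With these in place all 14 subjects per cohort can count, up to 84 in Part B, subject to the ordinary EP and PP rules. The cost is text in a protocol amendment and a SAP revision, with no added visits, samples or subjects. The changes should be dated before any review of deviations, so that population membership is fixed without reference to responses.

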## **9.2 Subject Exclusion Criteria**

Subjects who meet any of the following criteria will not be eligible to participate or continue further in the study:

1. Have received prior standard therapy regimens within 4 weeks of Day 1;

2. Have received prior treatment with monoclonal antibodies within 6 weeks of first dose of Day 1;
3. Have had major surgery within 30 days prior to the start of Day 1;
4. Received any investigational treatment within 4 weeks prior to the start of study medication;
5. Have had an infection requiring the use of parenteral antibiotics within 14 days prior to the start of Day 1;
6. Have known central nervous system metastasis or CNS lymphoma;
7. Is receiving corticosteroids (>10 mg prednisone daily or equivalent);
8. Has known bleeding diathesis that could be considered a safety concern;
9. Has a history of other malignancy within the 3 years prior to screening, except adequately treated basal cell or squamous cell carcinoma of the skin, or carcinoma in situ;
10. Has difficulty swallowing medications, or known history of malabsorption syndrome;
11. Has a serious concurrent medical condition, such as:
  - a. History of congestive heart failure New York Heart Association (NYHA) class III or IV,
  - b. 12-Lead ECG abnormalities considered by the investigator to be clinically significant or QTcF  $\geq$  450 milliseconds at screening. Abnormal values may be confirmed from one additional assessment. For subjects with QTcF  $\geq$  450 on initial screening ECG, the mean of the two QTcF assessments will be used to determine eligibility;
  - c. Myocardial infarction, angioplasty, or cardiac stent placement within the last 6 months,
  - d. HIV infection,
  - e. Known Hepatitis B or C infection. Subjects at high risk for Hepatitis B or C infection should have serology testing to rule out infection;
  - f. A medical condition requiring the therapeutic use of anticoagulants
  - g. Condition or situation which may put the subject at significantly increased risk, may confound the study results, or may interfere significantly with the subject's participation in the study
12. Known hypersensitivity to ASN002 or its excipients;
13. Prior participation, i.e., receipt of study medication, in this study;
14. Any condition that, in the opinion of the investigator, would impair the subject's ability to comply with study procedures;
15. Subjects that are pregnant or lactating;

16. Part B only: Prior treatment with SYK or JAK inhibitors, except for subjects with myelofibrosis treated with a JAK inhibitor.

### **9.3 Subject Discontinuation Criteria**

Study discontinuation will occur when a subject who signed informed consent ceases participation in the study. Subjects can be discontinued from the study for one of the following reasons:

- An adverse event;
- Progression of disease;
- Death;
- A protocol violation (reason must be specified, for example: lack of compliance, use of a prohibited concomitant medication, failure to meet inclusion/exclusion criteria after study entry, etc.);
- Withdrawal of consent by the subject (reason must be specified);
- The subject was “lost to follow-up”;
- Other reasons (reason must be specified, for example: the subject moved, investigator decision, sponsor decision to terminate study, etc.).

A subject is free to withdraw his consent and discontinue participation in the study at any time. The investigator must withdraw any subject from the study if the subject requests to be withdrawn. Any subject who withdraws consent as a result of an adverse event, regardless of intensity or investigator's opinion, must be reported as a discontinuation due to adverse event.

If a subject discontinues from the study, all end of treatment procedures should be conducted as detailed in **Table 1** or **Table 2**. The date a subject discontinues ASN002, and the reason for discontinuation will be recorded in the source documentation and electronic Case Report Form (eCRF). If a subject has an ongoing adverse event, the event will be followed until resolution or stabilization for at least 30 days after the last dose of ASN002. If a subject refuse to complete any of the specified End of Treatment procedures, this information will be recorded in the source documentation. A subject who discontinues from the study will not be allowed to re-enter the study.

When a subject is “lost to follow-up” (i.e., fails to return for study visits), a reasonable effort will be made to contact the subject:

1. to determine the reason for the failure to return and these contacts will be recorded in the source documents;
2. to follow up on any ongoing AEs from the previous visits;
3. to recover any unused ASN002.

The subject should be identified as “lost to follow up” in the eCRF, as appropriate.

### 9.3.1 Replacement Procedures

During Part A, a subject who prematurely discontinues from the study before completing 28 days of the dose escalation component for reasons other than DLT, or has demonstrated significant non-compliance with ASN002 dosing, may be replaced at the discretion of the sponsor. Subjects participating in Parts B who discontinue from the study due to non-compliance or protocol violations may be replaced at the discretion of the Sponsor.

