#### Part B:

A sample size of 84 subjects (14 each in DLBCL, MCL, FL, PTCL, MF and CLL) will be enrolled. The null hypothesis that the true response rate is 0.05 will be tested against a one-sided alternative. A total of 14 patients will be accrued in each cohort. The null hypothesis will be rejected if at least 3 responses are observed in 14 subjects. This design yields a type I error rate of 0.02 and power of 0.9 when the true response rate is 0.4.

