### **3 STUDY DESIGN**

#### **3.1 Overall Study Design and Treatment Groups**

This study will be performed at approximately 3 to 15 study centers located in the United States and Latin America.

The study is an open-label, non-randomized, uncontrolled, multicenter, dose escalation, cohort expansion and extension study with single and multiple-dose PK in subjects with relapsed/refractory lymphomas, MF, CLL, and advanced/metastatic solid tumors for which no standard therapy exists. The study will be conducted in 2 parts:

Part A: Evaluation of the safety and tolerability of escalating multiple doses of ASN002;

Part B: Cohort expansion of 6 identified disease-specific cohorts (DLBCL, MCL, FL, PTCL, MF and CLL) from Part A to further evaluate the safety, tolerability and antitumor activity of multiple doses of ASN002.

Part A will be a “3+3” dose escalation scheme beginning with dose level 1 at a dose of 10 mg every 12 hours. Subjects will receive a single dose of ASN002 on Day 1, followed by every 12 or 24 hours, as assigned, dosing beginning on Day 3. The dose of ASN002 will be escalated to identify DLTs, and the MTD. If an MTD is not identified by the last scheduled cohort, dose escalation will continue in less than or equal to 50% increments until the MTD is identified. If supported by the PK profile, transition to once daily dosing may be considered. The starting dose of the once daily (qd) dosing cohorts will not exceed the total daily dose of the highest twice daily dose that is considered safe and well tolerated. Daily dosing cohorts may include doses beginning at 60 mg QD. Additional dose escalation may be performed for the qd dose cohorts, if the MTD is not identified by the 100 mg qd dose.

The study design includes a screening period (up to 28 days), and a DLT observation period of 28 days (Cycle 1). A subject with no DLTs during Cycle 1 will have the opportunity to continue to receive ASN002, at the discretion of the investigator. Subjects that are not able to complete Cycle 1 for reasons other than DLT will be replaced. Subjects participating in Parts B who discontinue from the study due to non-compliance or protocol violations may be replaced at the discretion of the Sponsor. Subjects may

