## **9.1 Evaluation of Disease Status**

### **9.1.1 DLBCL, MCL, FL, PTCL**

For cohorts that have at least 5 subjects at the recommended Part B dose of 75 mg BID, the frequency of responders according to the 2014 Lugano Classification for subjects with lymphoma will be evaluated at each dose level and for each lymphoma subgroup in Part B. Differences in response to therapy based on the molecular subtypes of DLBCL will be explored.

Assessments will be made after every two 28-day cycles of therapy, i.e., starting just before Day 1 of cycle 3 and then just before each odd-numbered cycle, for solid tumor patients and after every 3 cycles, i.e., just before Day 1 of cycle 4 and then just before cycles 7, 10, and 13, etc, for lymphoma patients.

In Part B, response to treatment will be analyzed using the binomial test for each of the disease-specific cohorts (DLBCL, MCL, FL, PTCL, MF and CLL). The dichotomous classifications to be assessed in each binomial test are disease responders versus non-responders. Responders will be considered as subjects with 2014 Lugano Classifications given by Complete Response (CR) or Partial Response (PR), and non-responders as subjects with 2014 Lugano Classifications given by No Response (NR) or Stable Disease (SD), or Progressive Disease (PD). For each binomial test, the null hypothesis is that the rate of disease responders is 5% and the one-sided alternative hypothesis is that the rate of disease responders is greater than 5%. The null hypothesis will be rejected if the p-value is less than 0.05 (i.e., using a one-sided significance level of 0.05).

Summaries for best disease response will be provided by treatment cohort for subjects diagnosed with lymphoma using frequencies (counts and percentages). For Part B, the estimated rate of disease responder and the p-value from the binomial test will be provided by disease-specific cohort (DLBCL, MCL, FL, PTCL, MF and CLL).

Response to treatment will be provided in a data listing by subject.

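### Part B replacement is discretionary and not blind to response, and replaced subjects can also leave the primary population, so selective replacement could raise the observed response rate and the type I error

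*Protocol*

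**What the plan says.** **Replacement.** Protocol 9.3.1 provides that Part B subjects who "discontinue from the study due to non-compliance or protocol violations may be replaced at the discretion of the Sponsor". Protocol 8.1 has the same rule, and SAP 3.1 repeats it in a sentence opening "Subjects participating in Parts B who". None of the three gives a time limit for Part B or requires the decision to be made without knowledge of response. The Part A clause on early discontinuation in 9.3.1, by contrast, is tied to the first 28 days.

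**What counts as a violation.** Protocol 9.3 gives these examples: "lack of compliance, use of a prohibited concomitant medication, failure to meet inclusion/exclusion criteria after study entry".

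**Who is analysed.** Protocol 15.2 and SAP 5.3 make PP the primary efficacy population. PP is the Efficacy Population (EP) without major violators, and EP requires an evaluable tumour assessment at screening and after dosing. SAP 8.3 names, in an open-ended list, entry-criteria failures, prohibited concomitant medication and repeated non-compliance as major deviations. They are to be identified before database lock; blinding to response is not mentioned.

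**The test.** Protocol 15.1 plans 14 subjects per cohort, takes 0.05 as the null response rate with a one-sided test, and fixes the decision as a count: "The null hypothesis will be rejected if at least 3 responses are observed in 14 subjects". SAP 9.1.1 runs a binomial test in each cohort at one-sided 0.05. Protocol 15.10 and SAP 12 say that analyses will be done on an ongoing basis because the study is open-label.

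**The concern.** A rule of 3 responses in 14 has its nominal properties only if membership of the 14 does not depend on response. Here the sponsor decides on replacement case by case while responses can be seen. The three examples of a violation in Protocol 9.3 reappear in SAP 8.3 as possible major deviations, so the ground for replacing a subject can also be the ground for dropping that subject from PP. The first subject then leaves the primary analysis and a new one enters with a fresh chance to respond.

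Some of these grounds could plausibly track outcome. Protocol 10.6.1 prohibits chemotherapy, radiotherapy and immunotherapy, which a subject doing badly may be more likely to receive. Protocol 10.7 leaves withdrawal for repeated non-compliance to the investigator's judgement. With 14 subjects, one response can decide whether a cohort counts as positive.

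**Working it through.** **Inputs from the documents.** Null rate 0.05, alternative rate 0.40, n = 14 and rejection at 3 or more responses (Protocol 15.1); one-sided level 0.05 (SAP 9.1.1); no multiplicity adjustment (SAP 6.4).

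**Assumption, not in the documents.** k is the number of non-responders per cohort who are replaced because they did not respond and are excluded from PP. Range shown: 0 to 3.

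**Step 1: the plan's own figures.** Protocol 15.1 says: "This design yields a type I error rate of 0.02 and power of 0.9 when the true response rate is 0.4". The exact binomial for 3 or more of 14 gives:
- at 0.05: 1 − 0.95^14 − 14(0.05)(0.95^13) − 91(0.05²)(0.95^12) = 0.0301, against 0.02 stated;
- at 0.40: 0.9602, against 0.9 stated.

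Neither figure reproduces. The closest match among the variants tried is 3 or more of 12 (0.0196 and 0.9166), which suggests, by inference only, that the text quotes figures for 12 subjects. That is a separate error. The baseline used below is 0.030.

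**Step 2: selective replacement.** Draw 14 subjects, then replace k non-responders once each. The final 14 hold 3 or more responders exactly when 14 + k draws contain 3 or more responses, because with fewer than 3 responders there are always at least k non-responders to replace. So:
- P(reject) = P(Bin(14 + k, 0.05) ≥ 3);
- expected observed rate at a true 0.40 ≈ (14 + k) × 0.40 / 14.

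| k | P(reject) at 0.05 | Expected rate at true 0.40 |
|---|---|---|
| 0 | 0.0301 | 0.400 |
| 1 | 0.0362 | 15 × 0.40/14 = 0.429 |
| 2 | 0.0429 | 16 × 0.40/14 = 0.457 |
| 3 | 0.0503 | 17 × 0.40/14 = 0.486 |

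With the same k in all six cohorts, and cohorts independent, the chance of at least one false-positive cohort is 1 − (1 − P)^6: 0.167, 0.199, 0.232 and 0.266 for k = 0 to 3.

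**Step 3: replacement unrelated to response.** The final 14 are still 14 independent draws at the true rate. The error stays at 0.0301 and the expected rate at 0.40.

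**Step 4: all dosed subjects kept, p-value on actual n.**

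| n | p-value for 3 responses | Responses needed at 0.05 | Type I error | Power at 0.40 |
|---|---|---|---|---|
| 14 | 0.0301 | 3 | 0.0301 | 0.9602 |
| 15 | 0.0362 | 3 | 0.0362 | 0.9729 |
| 16 | 0.0429 | 3 | 0.0429 | 0.9817 |
| 17 | 0.0503 | 4 | 0.0088 | 0.9536 |

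The level stays below 0.05 at each n, provided that the final n was not itself chosen on response.

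**The case against.** **The clause is narrow.** Protocol 9.3 lists progression, adverse events, death, withdrawal of consent and loss to follow-up as separate reasons for discontinuation, and Part B replacement is offered for none of them. Progression is the usual exit for a non-responder: Protocol 6.3 reports it for 13 of 21 Part A discontinuations. Entry failures and over-dosing need not track response. This stands, and it limits how large k can plausibly be.

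**Replacement alone removes nobody.** Section 9.3.1 says nothing about analysis sets. Exclusion comes from the PP definition, whether or not the subject is replaced, and a replaced subject with evaluable assessments stays in the supportive EP. This also stands. It is why the remedy addresses the primary population as well as the replacement clause. EP is not full protection, because a subject without an evaluable post-dose assessment is outside it too.

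**There may be no result to select on.** Lymphoma is first assessed at 12 weeks, so an earlier stopper has no scheduled on-treatment result. This stands in part. CLL is assessed every 8 weeks and MF spleen size by palpation every 4 (Protocol Table 2), and Protocol 10.4 includes a disease assessment at end of treatment.

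**The remedy does not move the rejection rule at k = 1 or 2.** Correct: 3 of 15 and 3 of 16 still reject. At those values it corrects the estimate and the reported p-value; the critical count changes only at n = 17.

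**There is some transparency already.** Discontinuation reasons, major deviations and responses are to be summarised or listed. That lets a reader see a replacement afterwards but does not prevent selection.

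**Conclusion.** The concern holds as a conditional one. The plan permits response-dependent replacement and supplies a route by which a dosed non-responder leaves the primary analysis. Under the assumption of 1 to 3 selective replacements per cohort, type I error goes from 0.030 to between 0.036 and 0.050, and a true rate of 0.40 would be observed on average as about 0.43 to 0.49. One or two such replacements keep a cohort under the SAP's 0.05; three put it just above.

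A reader might infer more than the documents support:
- That error and response rate will rise. They rise only if replacement depends on response, and nothing shows that it will.
- That any non-responder can be exchanged. Those who stop for progression or an adverse event cannot be replaced under this clause.
- That the 10% early-termination rate in Protocol 8.2 gives the size of the effect. That rate covers all causes and is used to go from 148 to about 163 subjects; it is not a replacement rate. The documents give no value for k.

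The effect on error is modest and the objective is preliminary efficacy, but the change is small enough that it should be made.

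**What to change.** 1. **SAP 5.3 and 9.1.1:** make the primary Part B response analysis include every dosed subject in the cohort, whether or not replaced and whether or not a major violator. Use the documented response, and count the subject as a non-responder if there is none. Compute the binomial p-value on the actual n. Keep PP as supportive. Align Protocol 15.2, which also names PP as primary.
2. **Protocol 8.1 and 9.3.1, SAP 3.1:** state that decisions to replace dosed Part B subjects are made without regard to response, and that each replacement and its reason are reported. The level in step 4 of the working depends on this.
3. **Protocol 10.7 and SAP 8.3:** the upper compliance limits differ (100% and 105%). Reconcile them, since they bear on who may be withdrawn and who is classed as a major violator.

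The cost is a few sentences in each document. Cohorts with replacements or unassessed subjects will report a slightly lower response rate and be tested on n slightly above 14; at n = 17, 4 responses are needed instead of 3, with power 0.954 at a true rate of 0.40. The sponsor can still enrol replacements.
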